4.3.2. Inclusion and exclusion criteria

Inclusion criteria: Participants must meet all of the inclusion criteria below at screening to participate in this study.

1. Age 65-85, male and female
2. Meet the National Institute of Aging – Alzheimer’s Association core clinical criteria for mild cognitive impairment or probable Alzheimer’s disease dementia with a Clinical Dementia Rating (CDR) score of 0.5-1 and MMSE score of 20-28
3. Report a history of subjective memory decline with gradual onset and slow progression over the last one year before screening; MUST be corroborated by an informant
4. On cholinesterase inhibitor therapy for Alzheimer’s disease (AD) and must be on a stable dose for at least 12 weeks prior to baseline
5. Caregiver/study partner that can accompany participant to all study visits
6. Sufficient English language skills to complete all tests
7. Sufficient vision and hearing to complete all tests
8. No known allergies to *Centella asiatica*, Maltrin-100, coconut sugar, citric acid, malic acid, caramel color or any of their derivatives
9. Willingness to discontinue all botanical dietary supplements for one week prior to and during each study visit
10. Willingness to comply with a 48-hour low plant diet for each study visit
11. Absence of significant depression symptoms (Geriatric Depression Scale-15 score of <12)
12. Body Mass Index (BMI) greater than 17 and less than 35 at screening
13. General health status that will not interfere with the ability to complete the study

Exclusion criteria: All candidates meeting any of the exclusion criteria below at baseline will be excluded from study participation.

1. Current smoking, alcohol or substance abuse according to DSM-V criteria
2. Women who are pregnant, planning to become pregnant or breastfeeding
3. Men who are actively trying to conceive a child or planning to within three months of study completion
4. Severe aversion to venipuncture
5. Abnormal laboratory evaluation indicating asymptomatic and untreated urinary tract infection
6. Cancer within the last five years, with the exception of localized prostate cancer (Gleason Grade <3) and non-metastatic skin cancers
7. Comorbid conditions such as diabetes mellitus, kidney failure, liver failure, hepatitis, blood disorders, clinical symptomatic orthostatic hypotension, and unstable or significantly symptomatic cardiovascular disease
8. Significant disease of the central nervous system such as brain tumor, seizure disorder, subdural hematoma, cranial arteritis, or clinically significant stroke
9. Major depression, schizophrenia, or other major psychiatric disorder defined by DSM-V criteria

10. Medications: sedatives (except those used occasionally for sleep), central nervous system active medications that have not been stable for two months (including beta blockers, cimetidine, SSRIs, SNRIs), anticoagulants (i.e. Warfarin), investigational drugs used within five half-lives of baseline visit, systemic corticosteroids, neuroleptics, anti-Parkinsonian agents, narcotic analgesics, nicotine (tobacco, patches, gum, lozenges, etc.), *Cannabis sativa* (herb or edibles)
11. Non-Alzheimer dementia such as vascular dementia, normal pressure hydrocephalus or Parkinson's disease
12. Mini Mental State Examination (MMSE) score of <20 or >28 or CDR score >1 or zero
13. Unwilling to maintain stable dosage of AD medications throughout study duration
14. Inability or unwillingness of individual or legal guardian/representative to give written informed consent.
15. Current drug or alcohol use or dependence that, in the opinion of the site investigator, would interfere with adherence to study requirements.

4.3.3. Vulnerable populations

Our study population includes mildly demented elders. The signing of the consent form will follow guidelines from sections of the Code of Federal Regulation regarding protocols that involve decisional impaired adults. Whenever possible, consent will be obtained from the subject, assent must always be obtained directly from the subject. We will have an IRB approved plan (a Decisionally Impaired Adult Supplement) to utilize surrogate consent by a legally authorized representative (LAR) if the subject gives assent but is not capable of signing consent. The LAR may be different from the study partner. In accordance with OHSU POLICY HRP-021, the following individuals may serve as an LAR for an adult subject who lacks capacity to consent, in order of priority:

- 1) Health care representative who is legally authorized by a valid advance directive or health care power of attorney
- 2) Court-appointed guardian
- 3) If the above two do not exist or cannot be located with reasonable effort, another surrogate who knows and can represent the previously expressed wishes of the potential subject, in the following order of preference:
 - a) Spouse or registered domestic partner
 - b) Adult child
 - c) Either parent
 - d) Adult sibling
 - e) Adult designated by others on this list, if no one on the list objects
 - f) Other adult relative or friend who has an established relationship with the potential subject

A signature line has been included in the participant consent form for the LAR. The LAR will co-sign consent for subjects capable of signing consent at the start of the study, in case the subject's cognitive impairment worsens over the course of the study. If the subject is not capable of signing consent, the LAR will sign the consent form only after the subject gives assent for participation.

Based upon the age range needed in our study population, children will be excluded. We will exclude women who are pregnant, planning to become pregnant or breast-feeding. We will also exclude prisoners. We will not exclude any ethnic group.

4.4. Setting

All participants will be enrolled at Oregon Health and Science University (OHSU) and the OHSU Institutional Review Board (IRB) will oversee the study. There will be no additional sites for this

study. All screening and study visits will be conducted at the Oregon Clinical and Translational Research Institute's Clinical and Translational Research Center (CTRC). Screening visits will occur in the equipped outpatient rooms and the study visits will occur in the infusion suite of the CTRC. All plasma and urine storage will occur in a -70°C freezer in [name] laboratory in the Biomedical Research Building and processing will occur in [name] laboratory in Richard Jones Hall at OHSU. All sample analysis will occur at the Bioanalytical Shared Resource/Pharmacokinetic Core (BSR/PK) in Richard Jones Hall at OHSU and/or the mass spectrometry service at Oregon State University.

4.4.1. Data management

We will use the Oregon Clinical and Translational Research Institute's installment of REDCap to manage the data and prevent data corruption or loss. All analyzed data will be stored in a password-protected folder on OHSU's X-drive. All paper case report forms, consent forms and questionnaires will be scanned into the participant's REDCap entry. Only people directly involved with the study will be granted access to the REDCap database and X-drive with access specific to their role in the project as determined by the Principal Investigator.

4.5. Institutional Review Board (IRB) review

This protocol and the informed consent document and any subsequent modifications will be reviewed and approved by the IRB or ethics committee responsible for oversight of the study.

5. INTERVENTION

5.1. *Centella asiatica* water extract product (Figure 4) (information on the preparation method is confidential/proprietary): *Centella asiatica* dried herb (aerial parts) was purchased through Oregon's Wild Harvest (OWH; Redmond, OR) and authenticated by organoleptic analysis, thin layer chromatography (TLC), and high-performance liquid chromatography-tandem mass spectrometry (HPLC-MS/MS). Heavy metal testing of the raw herb and a pilot hot water extraction at OHSU was performed to ensure low levels of all heavy metals and compliance with the Food and Drug Administration (FDA) and American Public Health Association's (APHA) limits. Pharmachem Laboratories (PCL; Kearny, NJ), a Good Manufacturing Practice (GMP) certified facility, performed a large-scale hot water extraction of *Centella asiatica* using a standardized protocol. The water extract was spray dried onto a food grade maltodextrin matrix at PCL and then shipped to OWH for blending with a food-grade sweetening and coloring agent before packaging into individual dose sachets. To yield different doses (equivalent to 2g and 4g of water extract) the maltodextrin matrix, coloring agent and flavoring agent (excipients) were blended in appropriate ratios so that each dose will contain the same amount of the excipients but different amounts of the water extract. The final product is to be referred to as *Centella asiatica* product (CAP) and is to be reconstituted in ten to twelve ounces of room temperature water and consumed by mouth once daily. Samples of the raw herb, extract and product have been retained for fingerprinting using high-performance liquid chromatography-mass spectrometry (HPLC-MS) and voucher samples deposited in [name] (PI) laboratory and the Oregon State University Herbarium.

OWH will send the sachets of intervention to the OHSU Research Pharmacy for storage at in the freezer (-20°C) and dispensing following the Pharmacy's applicable policies and procedures. [name], members of the study team, and the mass spectrometry service at Oregon State University will perform quality control and stability assessments throughout the study. The study has received Investigational New Drug (IND) approval from the FDA (136099). The drug will be used in compliance with the requirements of HRP-815.

5.2. Dispensing

Each sachet will be dispensed to a member of the study team just prior to the participant's study visit and recorded by the Pharmacy staff including the date, participants ID number and dosage for accountability. Participants will receive two single administration doses of the *Centella asiatica* product equivalent to 2g and 4g of *Centella asiatica* water extract. The order in which they receive these doses will be random to prevent a tolerance effect. The doses selected are based on allometric scaling¹³¹ from previous murine studies, which showed that 1.4 g/day of *Centella asiatica* water extract for a 70 kg human was equivalent to the 200 mg/kg/day estimated intake in mice. Participants will consume CAP in the presence of a member of the research team following baseline measurements, in order to ensure adherence to the study protocol.

5.3. Destruction

Following study completion, the remaining intervention sachets will be provided to [name] for destruction.

[figure not shown]

Figure 4. Process of product and placebo manufacture.

*OWH = Oregon's Wild Harvest (Redmond, OR); PCL = Pharmachem Laboratories (New Kearny, NJ); OHSU = Oregon Health and Science University (Portland, OR); OSU = Oregon State University; *Excipients = additional maltodextrin, coconut sugar, malic acid, citric acid, caramel color.

5.4. Accountability

The OHSU Research Pharmacy will dispense following the Pharmacy's applicable policies and procedures. Each dose and dispensing will be documented in the Pharmacy's electronic database, which utilizes a time and signature stamp. See Manual of Operations for further instructions on appropriate accountability documentation methods.

5.5. Adherence assessment

Participants will consume single doses of CAP in the presence of a member of the research team following baseline measurements, in order to ensure adherence to the study protocol.

5.6. Randomization, blinding and stratification

Randomization: Randomization will use an arm equivalence design to promote equal numbers of participants for each order schema. Randomization will occur within 72 hours of completion of the screening and baseline assessments collected at the screening visit and 72 hours prior to study intervention initiation. The order in which the doses are administered will be randomized so that some data will be available for both doses in case of dropouts after the first visit.

Blinding: All participants will be blinded to the dose they will be receiving at each visit. We have developed a formulation that tastes and looks very similar at each dose. The investigator administering the intervention and the analyst performing the LC-MS analysis of collected plasma will be blinded as to the dose of the product administered. The LC-MS analyst will also be blinded as to the time point of collection. The principal investigator, [name], is authorized to break the blind.

Stratification: Participants will be stratified by gender so that each dose level (2g or 4g) is administered to equal numbers (n=8) of each gender. Although exploratory in nature, contrasts between gender and cognitive impairment status will be calculated for powering and pilot data purposes.

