 - Safety and tolerability of single doses of CAP determined by participant interviews, biometrics, electrocardiography, laboratory assessment of liver and kidney function, vital signs and questionnaires
 - The level of triterpenes, caffeoylquinic acids, and their metabolites in a pooled urine sample collected over 10 h after CAP administration.
 - Activation of the NRF2 antioxidant response element pathway in peripheral blood mononuclear cells (PBMC) over 6 hours following CAP administration.

Intervention and duration

This is a study using a product composed of a water extract of the botanical *Centella asiatica*. The C_{max} , T_{max} and other pharmacokinetic parameters and tolerability assessments of two doses of CAP (2g and 4g) will be compared to one another. Participants will be in the study for up to two months. The minimum time a participant could be on study would be six weeks.

Sample size and population

The target population is elders aged 65-85 years old with a diagnosis of mild cognitive impairment for which they are currently on cholinesterase inhibitor therapy. There will be 4 male and 4 female participants in the study. This is a randomized crossover study, so no stratification will be implemented in randomization.

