4.3. Study Population

4.3.1. Number of participants

Eight mildly demented elderly volunteers on cholinesterase inhibitor therapy (n=4 each female and male) 65-85 years of age will be screened and enrolled in the study. We estimate that we will need to screen approximately twelve potential participants to meet the eight volunteers needed to complete the study. We anticipate a possible dropout rate of 1 participant (14%) However, we are still powered to see differences between doses with a 25% drop out rate resulting in 6 remaining subjects.

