6. SCREENING AND STUDY ACTIVITIES

6.1. Candidate identification

We require equal numbers of male and female elderly subjects (age 65-85). These would include 8 individuals with amnesic mild cognitive impairment (MCI) or mild Alzheimer's disease (AD).

We will utilize the following resources available at OHSU to identify potential subjects:

- Oregon Alzheimer Disease Center (OADC) registry of subjects enrolled in a longitudinal study;
- NeuroNEXT database (an NINDS initiative to conduct/foster exploratory trials in neurological conditions). [name] (Co-PI) has access;
- OHSU's patient database EPIC using the "Cognos" searching tool.

The table below gives the numbers of subjects that *prima facie* would qualify for our study from these sources.

Table 4. Recruitment resources

Resource	Number of mild AD subjects ^[SEP] Age 65-85
OCTRI research volunteer repository Research Match	0 with known MCI/AD
OADC subjects registered in an NIA funded longitudinal study and who have consented to being approached for clinical trials. Mild AD or MCI (age 65-85; CDR 0.5-1 and MMSE 20-28): ^[SEP] 38 women, 20 men, of which 13 women, 11 men are OHSU patients.	38 women and 20 men, of which 10 women and 6 men are already OHSU patients. CDR 0.5 to 1 MMSE 20-25
NIH/NINDS Neuronext database of subjects interested in taking part in dementia research	11 women and 10 men who registered with clinically confirmed diagnoses of MCI
Data from Cognos search of EPIC ^[SEP] Feasibility of in-clinic recruitment for OHSU's Layton Center for Alzheimer's and Aging based on visits over the last 12 months	40 women and 37 men with confirmed MCI were seen at OHSU in the last 12 month
Totals assuming no overlap between recruitment tools	89 women, and 67 men

If we require additional subjects beyond the number we can recruit from these sources, we will use additional methods. For example, the Oregon Clinical and Translational Research Institute at OHSU also provides other recruitment tools such as "Research Data Warehouse" and "Cohort Discovery".

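### Section 5.6 stratifies randomisation by gender while the synopsis rules stratification out, and its count of 8 per gender does not fit 4 men and 4 women; if the synopsis governs, dose order may be unbalanced within gender

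*Combined protocol and SAP*

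**What the plan says.** The stratification paragraph of section 5.6 reads: "Participants will be stratified by gender so that each dose level (2g or 4g) is administered to equal numbers (n=8) of each gender". The synopsis, under sample size and population, reads: "This is a randomized crossover study, so no stratification will be implemented in randomization". Just before that it fixes the numbers: "There will be 4 male and 4 female participants in the study". Section 4.3.1 repeats four of each gender, and section 6.1 gives eight individuals in total.

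On allocation, sections 4.1 and 5.6 say "Randomization will use an arm equivalence design to promote equal numbers of participants for each order schema"; neither mentions balance of order within gender. On exposure, section 5.2 says "Participants will receive two single administration doses of the *Centella asiatica* product equivalent to 2g and 4g", so each participant takes both doses.

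Gender results are planned in three places. Section 2.1 commits to evaluating gender differences in bioavailability and pharmacokinetics. Section 5.6 plans gender contrasts and calls them exploratory. Section 10.8 allows that gender may prevent pooling, and states power of 75% (Cmax) and 67% (AUC) for the dose effect within one gender. Section 10.6 assesses dose dependence from within-subject differences and names no period or sequence term.

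**The concern.** Whoever builds the randomisation list cannot follow both rules. Section 5.6 also states its aim as equal numbers of each gender at each dose level. A two-period crossover achieves that automatically; what stratification has to protect is the order of doses within gender.

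If order is unbalanced within a gender, any systematic difference between visit 1 and visit 2 enters that gender's mean dose difference. No period term is planned to remove it. The results at stake are the within-gender dose effects, which section 10.8 treats as the fallback if the genders cannot be pooled, and the gender contrast.

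**Working it through.** **Count.** Each dose reaches every participant: 4 men + 4 women = 8 per dose. Eight of each gender would need 16 participants, against the 8 in the synopsis and in sections 4.3.1 and 6.1.

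**Which count the power statement fits.** The plan's critical t values reproduce for a two-sided paired t-test: 2.571 for n=6 (stated 2.57) and 2.447 for n=7 (stated 2.45). No standard deviation is given, so the standardised effects are back-solved from stated powers:
- Cmax: 86% at n=6 gives an effect of about 1.56.
- AUC: 83% at n=7 gives 1.33. If 86% is assumed, as for Cmax, it gives 1.38.

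| Within-gender n and test | Cmax power | AUC power |
|---|---|---|
| Stated in section 10.8 | 75% | 67% |
| n=4, one-sided | 76% | 65–68% |
| n=4, two-sided | 56% | 45–48% |
| n=8, two-sided | 96% | 89–92% |

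The stated figures are close to n=4 per gender and far from n=8. The agreement at n=4 needs a one-sided test, although section 10.6 specifies two-tailed significance. That is a separate matter. The check supports the count only, and it rests on back-solved effects.

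**Order by gender without stratification.** Assume order is held at 4:4 overall, as the design aims. There are C(8,4) = 70 equally likely allocations. The number that put k of the 4 men in the order 2g then 4g is C(4,k) × C(4,4−k):

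| Men in that order | Allocations | Probability |
|---|---|---|
| 2 (2:2 in each gender) | 36 | 51.4% |
| 1 or 3 (3:1 against 1:3) | 16 + 16 = 32 | 45.7% |
| 0 or 4 (complete confounding) | 1 + 1 = 2 | 2.9% |

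So P(3:1 or worse) = 34/70 = 48.6%.

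**Effect of imbalance.** Let d be the 4g minus 2g difference in one participant, δ the dose effect and π the visit 2 minus visit 1 effect. Then d has mean δ + π in the order 2g then 4g, and δ − π in the other order. With a of 4 in the first order, a gender's mean difference is δ + π(2a − 4)/4.
- 2:2: shift 0 in each gender, so the contrast carries 0.
- 3:1 against 1:3: shifts +0.5π and −0.5π, so the contrast carries 1π.
- 4:0 against 0:4: shifts +π and −π, so the contrast carries 2π.
- Pooled over genders with 4:4 overall: the shifts cancel in every case.

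**After one dropout.** Starting from 2:2, losing one participant's pair leaves 2:1. That gender's unadjusted effect then carries (2 − 1)/3 = one third of π. The pooled order split becomes 4:3 and carries (4 − 3)/7 = one seventh of π, whichever stratification rule was used.

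**Period adjustment without blocking.** Within one gender, the variance of the period-adjusted dose effect is proportional to (1/n1 + 1/n2)/4. This is 0.25 at 2:2 and 0.333 at 3:1, a third larger. At 4:0 the effect cannot be estimated within that gender.

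**The case against.** Read as a whole, section 5.6 nearly contains the right rule. Order is the only thing randomised in this crossover, so stratifying by gender can only sensibly mean order within gender. If section 5.6 governs on that reading, the imbalance does not arise. This stands: the 48.6% is conditional on following the synopsis.

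The count may be a misplaced total. Section 4.1 attaches n=8 to the two doses together, and 8 per dose fits 4 + 4. A reader might infer that the plan requires 16 participants; the enrolment statements and the power figures do not support that. This part is a wording correction, but the conflict over stratification remains on either reading of the count.

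A reader might also infer that dose is confounded with gender, or that the primary result is biased. Neither follows. Every participant receives both doses, and the pooled within-subject comparison is free of period bias while order is 4:4.

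The period effect is also hypothetical. The documents give no size for it, and the 48-hour diet with a diary, the 10-hour fast, the two-to-four-week washout and the comparison of baseline levels between visits all work to limit it. With four per gender, these results will be imprecise even under perfect balance. These points limit the importance of the concern. They do not settle which rule applies.

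**Conclusion.** The plan contains two incompatible randomisation rules and a count that is wrong as worded. If the synopsis rule is used, some order imbalance by gender is close to an even chance (48.6%), nearly all of it 3:1. Complete confounding is unlikely (2.9%), so it would overstate matters to say that order is confounded with gender by design.

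At 3:1, half the period effect enters each gender's unadjusted dose effect with opposite signs, and the whole of it enters the gender contrast. The consequence in concentration units cannot be given, because the documents state no period effect. The exposure is confined to the exploratory gender contrasts and the within-gender dose effects in section 10.8.

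The probabilities assume a 4:4 order allocation, which the arm equivalence design promotes but is not said to guarantee. Under independent coin-flip randomisation, 2:2 in both genders would occur with probability (6/16)² = 14.1%. It would also be too strong to say that stratified blocks remove the bias altogether: that holds only if all eight complete, and sections 4.3.1 and 10.8 anticipate one dropout.

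**What to change.** 1. Delete the synopsis sentence that rules out stratification.
2. In section 5.6, state that dose order is randomised within gender, in one block of four per gender with two participants per order.
3. In section 5.6, replace the count with 4 of each gender (8 in total) per dose.
4. In section 10.6, include a period term in the gender-specific analyses, to deal with imbalance left by dropout.

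The cost is wording, two blocks in the randomisation list and one model term; no extra participants or visits are needed. Within a single gender of four, the period term leaves 4 − 2 = 2 residual degrees of freedom. Fitting both genders together with a common period effect leaves 8 − 3 = 5, at the price of assuming that the period effect is the same in men and women. Enrolment is rolling (section 6.2), so the rule must be settled before the list is generated. If the sponsor prefers not to stratify, section 5.6 must still be corrected, and the period term becomes the only protection for the gender results.
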